### 4.2 Effectiveness Hypotheses

#### **Primary Effectiveness**

Document: TDOC-0055319

[figure not shown]
No inferences are to be made on the primary effectiveness endpoint; therefore, no hypotheses are formulated.

#### 4.3 Statistical Methods for Effectiveness Analyses

#### 4.3.1 Primary Effectiveness Analyses

Summary statistics will be provided at each visit (Dispense, 1-Day Follow-up, 1-Week Follow-up). Descriptive summary statistics will be displayed with counts and percentages on the Snellen categories, and n, mean, standard deviation, median, minimum, and maximum for the converted logMAR values.

Status: Effective

Version: 1.0; CURRENT; Most-Recent; Effective

Effective Date: 25-May-2018

# 5 Safety Analysis Strategy

Alcon - Business Use Only Statistical Analysis Plan

Document: TDOC-0055319

# 5.1 Safety Endpoints

The safety endpoints are

- Adverse events (AE)
- Biomicroscopy Findings/Slit Lamp Examination
  - Limbal hyperemia
  - Bulbar hyperemia
  - Corneal staining
  - Conjunctival staining
  - Palpebral conjunctival observations
  - Corneal epithelial edema
  - Corneal stromal edema

Effective Date: 25-May-2018 Alcon - Business Use Only Statistical Analysis Plan

Document: TDOC-0055319 Version: 1.0; CURRENT; Most-Recent; Effective

Status: Effective

Corneal vascularization

Conjunctival compression/indention

Chemosis

Corneal infiltrates

Other findings

Device deficiencies

#### 5.2 Safety Hypotheses

There are no formal safety hypotheses in this study. The focus of the safety analysis will be a comprehensive descriptive assessment of safety endpoints listed in Section 5.1.

#### 5.3 Statistical Methods for Safety Analyses

The analysis set for all safety analyses is the safety analysis set as defined in Section 2.1. Baseline will be defined as the last measurement prior to exposure to study lenses on Visit 1. Safety variables will be summarized descriptively.

#### 5.3.1 Adverse Events

The applicable definition of an AE is in the study protocol. All AEs occurring from when a subject signs informed consent to when a subject exits the study will be accounted for in the reporting.

Analysis and presentation of pre-treatment AEs will be separated from treatment-emergent AEs occurring during the study period. A pre-treatment AE is an event that occurs after signing informed consent but prior to exposure to the study lens. The period for treatmentemergent AE analysis starts from exposure to study lens until the subject completes or is discontinued from the study.

Descriptive summaries (counts and percentages) for ocular and nonocular AEs will be presented by Medical Dictionary for Regulatory Activities (MedDRA) Preferred Terms (PT). Serious AEs and significant nonserious ocular AEs will be noted. Additionally, relationship to lens will be identified in all AE tables. Unit of presentation for ocular AEs will be eye and nonocular AEs will be subject.

Individual subject listings will be provided for both pre-treatment and treatment-emergent AEs, where any AE leading to study discontinuation will be indicated.

Page 10 Printed By:

**Document:** TDOC-0055319 **Version:** 1.0; CURRENT; Most-Recent; Effective

Status: Effective

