- Fetal distress, fetal death, or a congenital abnormality or birth defect.

Alcon - Business Use Only Protocol - Clinical Effective Date: 22-Aug-2018

Document: TDOC-0054559 **Version:** 4.0; Most-Recent; Effective; CURRENT

Status: Effective Page 9 of 53

	Refer to Section 11 for additional SAEs.
Significant Non-Serious	Is a symptomatic, device-related, non-sight threatening
Adverse Event	adverse event that warrants discontinuation of any contact
	lens wear for greater than or equal to 2 weeks.
	Refer to Section 11 for additional Significant Non-Serious
	AEs.
Unanticipated Serious	Serious adverse device effect which by its nature, incidence,
Adverse Device Effect	severity or outcome has not been identified in the risk
(USADE)	management file.
Use Error	Act or omission of an act that results in a different medical
	device response than intended by manufacturer or expected
	by user. Note: This definition includes slips, lapses, and
	mistakes. An unexpected physiological response of the
	subject does not in itself constitute a use error.

Status: Effective Page 10 of 53

Effective Date: 22-Aug-2018

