11 ADVERSE EVENTS AND DEVICE DEFICIENCIES

11.1 General Information

An AE is any untoward medical occurrence, unintended disease or injury, or untoward clinical signs (including abnormal laboratory findings) in subjects, users, or other persons, whether or not related to the investigational medical device (test article). Refer to the Glossary of Terms and figures below for categories of AEs and SAEs.

[figure not shown]
Figure 11-1 Categorization of All Adverse Events

Effective Date: 22-Aug-2018 Document: TDOC-0054559 Version: 4.0; Most-Recent; Effective; CURRENT

Status: Effective Page 40 of 53

Figure 11-2 **Categorization of All Serious Adverse Events**

Serious Adverse Events

In addition to reporting all AEs (serious and non-serious) meeting the definitions, the Investigator must report any occurrence of the following as an SAE:

- An ocular infection including a presumed infectious ulcer with any of the following characteristics*:
 - Central or paracentral location
 - Penetration of Bowman's membrane
 - Infiltrates > 2 mm diameter
 - **Iritis** 0
 - Increase in intraocular pressure
 - Culture positive for microorganisms
 - Increasing size or severity at subsequent visits
- Any central or paracentral corneal event (such as neovascularization) that results in permanent opacification
- Hypopyon

Document: TDOC-0054559 **Version:** 4.0; Most-Recent; Effective; CURRENT

Status: Effective Page 41 of 53

- Hyphema
- Neovascularization within the central 6 mm of the cornea
- Permanent vision loss as defined by loss of 2 or more lines of BCVA from enrollment visit that fails to resolve
- Uveitis (anterior, intermediate, or posterior)
- Corneal abrasion affecting $\geq 50\%$ of corneal surface area

*NOTE: Culture samples (from the subject's eyes, lenses, etc) must be taken [as described in the MOP; and documented in the narrative section(s) of the corresponding ADE-SAE eCRF], for any suspected ocular infection, including infiltrates with overlying epithelial defect.

Significant Non-Serious Adverse Events

A significant non-serious AE is a device-related, non-sight threatening AE that warrants discontinuation of any contact lens wear for greater than or equal to 2 weeks. In addition, the Investigator must report any occurrence of the following as a Significant Non- Serious Adverse Event:

- Peripheral non-progressive non-infectious ulcers
- All symptomatic corneal infiltrative events

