- Corneal staining score greater than or equal to Grade 3 (Refer to MOP for grading scales)
- Temporary vision loss as defined by loss of 2 or more lines of BCVA from enrollment visit that persists for 2 or more weeks
- Neovascularization score greater than or equal to Grade 2 (Refer to MOP for grading scales)

The above events are based upon the categories provided in the ISO 11980 and the US FDA Premarket Notification (510(k)) Guidance Document for Daily Wear Contact Lenses.

Device Deficiencies

A device deficiency is inadequacy of a medical device with respect to its identity, quality, durability, reliability, safety, or performance. A device deficiency may or may not be associated with patient harm (ie, ADE or SADE); however, not all ADEs or SADEs are due to a device deficiency. The Investigator should determine the applicable category listed in the Device Deficiency eCRF for the identified or suspect device deficiency and report any patient harm separately. Examples of device deficiencies include the following:

Document: TDOC-0054559 **Version:** 4.0; Most-Recent; Effective; CURRENT

Status: Effective Page 42 of 53

• Failure to meet product specifications (eg, incorrect lens power/diameter/base curve/color)

- Lens cloudy
- Lens surface/edge defect
- Torn lens during handling/in pack
- Packaging deficit (eg, mislabeled product)
- Suspect product contamination
- Lack of performance

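### Do the two protocol wordings of a significant non-serious AE, and the SAP's reporting window ending at exit, leave the safety reporting unsettled?

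*SAP*

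**What the plan says.** SAP 5.3.1 has AEs summarised by Preferred Term as counts and percentages, with individual subject listings. On categories it adds "Serious AEs and significant nonserious ocular AEs will be noted". Its only pointer to a definition is "The applicable definition of an AE is in the study protocol", which covers the term AE and not this sub-category. Its reporting period is "All AEs occurring from when a subject signs informed consent to when a subject exits the study will be accounted for in the reporting".

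The protocol describes the sub-category in two places:

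- **Glossary (Section 1):** "Is a symptomatic, device-related, non-sight threatening" opens the definition, which goes on to require at least 2 weeks without lens wear. It then says "Refer to Section 11 for additional Significant Non-Serious" AEs.
- **Section 11.1:** "A significant non-serious AE is a device-related, non-sight threatening AE that warrants discontinuation of any contact lens wear", again for at least 2 weeks. Five further events follow that the investigator must report in the category. They include "All symptomatic corneal infiltrative events" and "Temporary vision loss as defined by loss of 2 or more lines of BCVA from enrollment visit that persists for 2 or more weeks".

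Protocol Section 11.6 deals with later information in three ways. Investigators should pass new safety information, including new AEs, to the sponsor. Follow-up on AEs still open at exit goes into the eCRF until database lock. Other data received within 1 month of exit are to be documented and made available if the sponsor asks.

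**The concern.** A condition that appears in one definition and not in the other can change how an event is classified, and the SAP does not say which wording governs. An example is easy to construct. Section 11.1 lists only symptomatic infiltrative events, SAP 5.1 records corneal infiltrates with no symptom condition, and protocol Section 11.2 makes a clinically relevant change in a study parameter an AE. An asymptomatic infiltrate that meets the remaining conditions would be flagged under Section 11.1 and not under the glossary.

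The reporting window raises a second question. An AE that begins after exit could be sent to the sponsor under Section 11.6 and yet have no visible SAP output. In addition, the listed vision-loss event needs 2 weeks of persistence, longer than the roughly 1 week of participation, so its status cannot be known at exit. At stake would be a complete and consistent account of notable ocular events in a small extended-wear study.

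**Working it through.** **1. Where the two definitions part.** Take an AE that is not serious and apply each text.

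| Event | Glossary | Section 11.1 | Same result? |
|---|---|---|---|
| On the Section 11.1 list | in (by cross-reference) | in | yes |
| Unlisted, symptomatic, device-related, non-sight-threatening, at least 2 weeks off lenses | in | in | yes |
| Unlisted, asymptomatic, otherwise as above | out | in | **no** |
| Unlisted, and either not device-related or less than 2 weeks off lenses | out | out | yes |

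Only the third row differs.

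**2. What happens to a third-row event in the outputs.** Under either wording it is counted under its Preferred Term, appears in the subject listing, and has its relationship to the lens identified, because SAP 5.3.1 asks for that in all AE tables. If it led to study discontinuation, the listing says so. If it is an infiltrate seen at a scheduled visit, it is also in the biomicroscopy grade table (SAP 5.3.2). Only the notation changes.

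**3. Size of the flag difference.** One eye in 22 is 1/22 = 4.5%, and one in 20 completers is 1/20 = 5.0%. These figures give scale only. SAP 5.3.1 plans percentages by Preferred Term and merely notes the significant non-serious events, so no planned percentage moves by this amount.

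**4. The reporting window against Section 11.6.**

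- AEs open at exit occurred before exit, so they are inside the SAP window. Their follow-up reaches the eCRF until lock.
- The request for new AEs carries no stated post-exit period and no analysis commitment.
- The 1-month provision asks for documentation and availability. It does not ask for eCRF entry.
- Protocol Section 12.6 promises AE summaries and a listing, with nothing specific to the period after exit.

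The SAP window is therefore narrower than what may reach the sponsor, but it contradicts none of these provisions.

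**5. Timing of late information.** Inputs: recruitment of about 3 weeks (protocol Section 8), so last enrolment near day 21; study completion at about 6 weeks (Section 7.1), day 42. Three assumptions are added: completion means database lock, recruitment is even, and 1 month is 30 days.

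| Visit 3 timing | Last exit | Days left to day 42 | Latest enrolment day e whose month ends by day 42 | Share running past day 42 |
|---|---|---|---|---|
| 7 days of wear (protocol Section 10) | 21 + 7 = 28 | 14 | e + 7 + 30 ≤ 42, e ≤ 5 | 16/21 = 76% |
| Same, using the -1 day window | 21 + 6 = 27 | 15 | e + 6 + 30 ≤ 42, e ≤ 6 | 15/21 = 71% |
| 7 days after Visit 2 (SAP Table 1-1) | 21 + 1 + 7 = 29 | 13 | e + 8 + 30 ≤ 42, e ≤ 4 | 17/21 = 81% |

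The time left for a 14-day vision-loss item beginning at the last exit is thus 13 to 15 days, on either side of what is needed depending on which visit text is read. The 71% to 81% shares concern data that Section 11.6 does not require in the database. If lock came after the last month had ended (28 + 30 = day 58, or 29 + 30 = day 59 on the SAP table), no subject's period would be cut off. The timing calculation therefore does not show that a planned output would be wrong.

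**The case for a change.** The strongest case for acting is that the ambiguity starts at the site. Investigators assign the category and about 2 sites are planned, so identical events could be classified differently before any programming. The glossary cites Section 11 only for additional events, so Section 11.1 is not said to override it. Settling the wording before unmasking would also avoid a later choice about a safety flag. The remedy would be cheap: one reconciled definition, a sentence on the information cut-off, and a listing that might be empty.

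Part of this stands. Both wordings are current, the SAP does not choose between them, and the documents do not show which is intended. But the event in question must satisfy a chain of conditions, the documents give no frequency for it, and it remains fully visible if it occurs. The glossary also sends readers to Section 11 for AE reporting requirements, so sites have one working section to follow.

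The case for a post-exit listing is weaker. Such events would be received passively, with no scheduled visit, and could reflect a return to habitual lenses. Parts of the SAP after 5.3.3, and the protocol's AE categorisation figure, are not shown, so the absence of a listing or a clarification cannot be established. As for the cut-off, an analyst would ordinarily use the eCRF as it stands at lock, which is where Section 11.6 sends follow-up on open AEs.

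**Conclusion.** No change to the plan is needed. The missing word is a drafting inconsistency in the protocol. It can alter one notation for a narrowly defined event, and it alters no AE count, no Preferred Term percentage and no conclusion. The post-exit point is a preference about reporting scope: the SAP states its window, AEs open at exit fall within it, and neither document commits to analysing events that begin later. The cut-off for the vision-loss item is a detail analysts can settle sensibly from the locked eCRF.

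This conclusion rests on the visible text of both documents and on the descriptive purpose of the study, which has no safety hypotheses. It does not depend on the timing assumptions.

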#### 5.3.2 Biomicroscopy Findings/Slit Lamp Examination

Biomicroscopy assessment will be performed at all study visits. The reporting unit for each biomicroscopy finding will be eye.

Effective Date: 25-May-2018

A summary of grade category counts and percentages will be presented for each parameter at each scheduled visit. Findings collected during unscheduled visits will be presented in a subject listing. Furthermore, a listing of "Other" slit lamp findings will also be provided.

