8.1 Inclusion Criteria

Written informed consent must be obtained before any study specific assessment is performed. Upon signing informed consent, the subject is considered enrolled in the study.

Subjects eligible for inclusion in this study must fulfill **all** of the following criteria:

1.	Subject must be at least 18 years of age and able to understand and sign an IRB/IEC
	approved Informed Consent form.
2.	Willing to attend all scheduled study visits as required per protocol.
3.	Successful wear of spherical soft contact lenses in both eyes during the past
	3 months for a minimum of 5 days per week and in an extended wear modality a

Version: 4.0; Most-Recent; Effective; CURRENT

Effective Date: 22-Aug-2018

Document: TDOC-0054559 Page 27 of 53 Status: Effective

	minimum of 1 night per week.
5.	Best spectacle corrected visual acuity 20/25 or better in each eye.

8.2 **Exclusion Criteria**

Subjects fulfilling any of the following criteria are not eligible for participation in this study.

1.	Any anterior segment infection, inflammation, or abnormality or disease (including			
	systemic) that contraindicates contact lens wear, as determined by the Investigator.			
2.	Any use of systemic or ocular medications for which contact lens wear could be			
	contraindicated, as determined by the Investigator.			
3.	History of ocular or intraocular surgery, including refractive surgery which contact			
	lens extended wear could be contraindicated, as determined by the Investigator			
	and/or history of irregular cornea.			
4.	Biomicroscopy findings at screening that are moderate (Grade 3) or higher and/or			
	corneal vascularization that is mild (Grade 2) or higher; or presence of corneal			
	infiltrate(s).			
5.	Current or history of pathologically dry eye in either eye that, in the opinion of the			
	Investigator, would preclude contact lens wear.			
6.	Current or history of herpetic keratitis in either eye.			
7.	Eye injury in either eye within twelve weeks immediately prior to enrollment for this trial.			
	tital.			
8.	Current or history of intolerance, hypersensitivity or allergy to any component of the			
	study products.			
9.	Current Biofinity lens wearer.			
10.	Any use of topical ocular medications and artificial tear or rewetting drops that			

Alcon - Business Use Only Protocol - Clinical Effective Date: 22-Aug-2018

Document: TDOC-0054559 **Version:** 4.0; Most-Recent; Effective; CURRENT

Status: Effective Page 28 of 53

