10 STUDY PROCEDURES AND ASSESSMENTS

Visit	Window
Visit 1, Day 1: Baseline/Dispense	N/A
Visit 2, Day 2: 1-Day Follow-Up	24 hours (±4 hours) after Visit 1
Visit 3, 1 Week: 1-Week Follow-Up/Exit	7 days (-1 day) of lens wear following insertion

Unscheduled Visits and Early Termination Visits are allowed, if necessary.

At the Baseline/Dispense Visit, study lenses will be dispensed contralaterally to the subject.			
All study lenses will be worn in an extended wear modality for approximately 6 nights.			
Problem lenses (if any) will not be discarded but collected by the subject and returned to the			
investigational site.			
. VA will be measured at all visits, and any decrease of two or			
more lines from the Dispense Visit to any follow-up visits should be explained by the			
Investigator.			

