10.4.2 Discontinuations

Discontinued subjects are individuals who voluntarily withdraw or are withdrawn from the study by the Investigator after signing the informed consent, including screen failures.

Subject numbers of discontinued subjects must not be re-used.

Document: TDOC-0054559 **Version:** 4.0; Most-Recent; Effective; CURRENT

Status: Effective Page 38 of 53

Subjects may discontinue from study or study treatment at any time for any reason. Subjects may also be discontinued from study treatment at any time if, in the opinion of the Investigator, continued treatment poses a risk to their health.

For subjects discontinuing from the study, the Investigator must complete all Exit procedures according to Table 3-1, Schedule of Study Procedures and Assessments, if the subject is willing and able, and if in the opinion of the Investigator it is safe for the subject to do so.

The Investigator must document the reason for study or treatment discontinuation in the subject's case history source documents.

To ensure the safety of all subjects who discontinue early, Investigators must assess each subject and, if necessary, advise them of any therapies and/or medical procedures that may be needed to maintain their health.

10.4.3 Schedule of Procedures and Assessments for Subjects Discontinued from Investigational Product

Other than screen failures, if a subject discontinues from the study the subject should undergo an Early Exit Visit. Refer to Table 3-1, Schedule of Study Procedures and Assessments.

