12.6 Safety Analyses

The safety endpoints are:

Document: TDOC-0054559 **Version:** 4.0; Most-Recent; Effective; CURRENT

Status: Effective Page 48 of 53

- AEs
- Biomicroscopy
- Device Deficiencies

There are no safety hypotheses planned in this study. The focus of the safety analysis will be a comprehensive descriptive assessment of occurrence of AE as well as the other listed parameters.

Descriptive summaries (counts and percentages) for ocular and nonocular AEs will be presented by Medical Dictionary for Regulatory Activities Preferred Terms. A listing containing details of the AEs will also be provided.

Each biomicroscopy parameter will be tabulated by its grade.

Frequency for each device deficiency category will be presented and a supporting listing will be provided.

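### Biomicroscopy is summarised only as grade counts per visit; adding a per-eye comparison with the baseline the SAP already defines would show how many eyes worsened within the grades admitted at entry

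*SAP*

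**What the plan says.** SAP 5.3.2 sets out the biomicroscopy summary: "A summary of grade category counts and percentages will be presented for each parameter at each scheduled visit". The reporting unit is the eye. Two listings are added, one for off-schedule findings ("Findings collected during unscheduled visits will be presented in a subject listing") and one for findings recorded as Other. Protocol 12.6 is shorter: "Each biomicroscopy parameter will be tabulated by its grade".

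SAP 5.3 defines a reference point for all safety variables: "Baseline will be defined as the last measurement prior to exposure to study lenses on Visit 1". Neither document has a readable output that sets an eye's later grade against that reference. There is no shift table, no count of eyes with a grade increase, and no listing of the graded findings at scheduled visits.

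Protocol 8.2, exclusion criterion 4, fixes which grades can be present at entry. Its general limit is worded "Biomicroscopy findings at screening that are moderate (Grade 3) or higher and/or". For vascularization the bar is one grade lower, at Grade 2, and any infiltrate at all excludes the subject. Grades below those limits are admitted.

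**The concern.** Biomicroscopy is one of the three safety endpoints, and neither document plans a safety hypothesis test, so the descriptive tables are the evidence. A count per visit gives the margins of a baseline-by-follow-up table. The number of eyes that got worse is a property of the cells inside that table, and the margins rarely fix it.

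The gap lies inside the admitted range. A finding above the entry limits at a scheduled follow-up visit must be new, because criterion 4 excluded it. Within the limits, an eye that reached a grade on the study lens looks the same in the tables as one that arrived with it. The subjects already wear lenses at least 5 days a week and overnight at least 1 night a week, so non-zero grades at entry are plausible, although the documents give no distribution.

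The fixed adverse event triggers in Protocol 11.1 (corneal staining of Grade 3 or higher, neovascularization of Grade 2 or higher) start just above the admitted range. A move from Grade 0 to Grade 2 staining meets no fixed trigger. It reaches the adverse event tables only if the investigator judges it clinically relevant under Protocol 11.2.

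**Working it through.** The plan gives no figure for this output, so there is nothing of its own to reproduce. The check is what the planned tables can and cannot determine.

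**Inputs**
- Eyes per lens: 20, the completion target in SAP Table 1-1 (about 22 are to be enrolled). Each subject contributes one eye to each lens.
- Grades admitted at entry: below Grade 3; vascularization below Grade 2; no infiltrates (Protocol 8.2, criterion 4).
- Parameters: SAP 5.1 names 11, apart from other findings. Only infiltrates must be absent at entry, so 11 − 1 = 10 can start above zero: 9 of them up to Grade 2, and vascularization up to Grade 1. This assumes that all use the grade scale of criterion 4. The scales are in the Manual of Procedures, which is not available.
- Grade counts: assumed throughout, since the documents give none.

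**Formula.** Let n be the eyes on a lens, a the number at Grade 2 at Visit 1, b the number at Grade 2 at Visit 3, and s the number at Grade 2 at both. No eye is above Grade 2 at Visit 1, so newly Grade 2 eyes = b − s. The tables give a and b but not s, which can lie anywhere from max(0, a + b − n) to min(a, b). Newly Grade 2 eyes therefore lie between max(0, b − a) and min(b, n − a).

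**Numbers, n = 20**

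| a = b | Newly Grade 2 eyes | Share of 20 |
|---|---|---|
| 2 | 0 to 2 | 0% to 10% |
| 4 | 0 to 4 | 0% to 20% |
| 5 | 0 to 5 | 0% to 25% |

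For a = b = 4, the answer follows the unseen s: 4 stay, 0 new; 3 stay, 1 new (5%); 2 stay, 2 new (10%); 0 stay, 4 new (20%). The last case is the extreme.

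**Whole grade distribution.** The smallest and largest numbers of worsened eyes were found over all tables with the given margins (grades 0/1/2, 20 eyes):

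| Visit 1 | Follow-up | Worse by 1 or more | Worse by 2 or more |
|---|---|---|---|
| 10/6/4 | 10/6/4 | 0 to 10 | 0 to 4 |
| 14/4/2 | 14/4/2 | 0 to 6 | 0 to 2 |
| 8/8/4 | 6/8/6 | 2 to 14 | 0 to 6 |
| 20/0/0 | 15/3/2 | exactly 5 | exactly 2 |

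The third row shows that the counts do carry information: a net shift, and a minimum of 2 worsened eyes. The fourth shows that the number is fixed when every eye starts at Grade 0. Otherwise the tables leave a range.

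**The case against.** The case against is substantial, and most of it stands as a limit on the point.

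- **The baseline is not ignored.** Biomicroscopy is done at Visit 1, which is a scheduled visit, so the planned tables should display the starting grades. A reader might infer that worsening is invisible. It is not: net shift and a minimum number of worsened eyes can be read. Only the comparison eye by eye is missing.
- **The design protects the lens comparison.** Each subject wears both lenses and the allocation to eyes is randomised, so grades present at entry are not expected to favour either lens. Visit 1 counts by lens would show a chance imbalance. The net comparison is fair without a shift table, but it does not say how many eyes worsened.
- **Clinically relevant change is captured.** Protocol 11.2 sends it to adverse event reporting, and SAP 5.3.1 tabulates ocular events by eye. What remains is change that the investigator judged not clinically relevant.
- **Early exits.** The protocol says "Unscheduled Visits and Early Termination Visits are allowed, if necessary" and that, on discontinuation, "the subject should undergo an Early Exit Visit". A reader might infer that those examinations fall into no planned output. Protocol 10.3 answers this: a visit between scheduled visits is documented as unscheduled, including one at which the subject discontinues, so its findings go to the listing. With about 22 subjects that listing can be read directly.
- **Treatment-emergent basis.** SAP 2.1 uses this term for the safety analyses, and a reader might infer that the missing shift table breaches it. The section explains the term by exposure and by the lens actually worn, and it promises no shift table.
- **Distinct eyes over Visits 2 and 3.** Per-visit counts do not give this number either, but the question does not arise for corneal staining, which is not graded at the lens-on Visit 2.

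**Conclusion.** The point holds as a modest improvement in reporting and not as an error in the plan. No readable biomicroscopy output compares each eye with the SAP 5.3 baseline, so the number of eyes that worsened within the admitted grades is generally not identifiable. With an assumed 4 of 20 eyes at Grade 2 at both visits and none higher, 0 to 4 could be new.

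The range rests on assumed counts, and its upper end needs complete turnover of the Grade 2 eyes with no change in their total. It shows what the tables leave open and does not predict a result. No error rate, sample size or hypothesis test is affected. The statement also depends on what can be read: the public SAP passes from 5.3.3 to Section 9, and Sections 6 to 8 could hold such an output.

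**What to change.** Before unmasking, add to SAP 5.3.2: for each biomicroscopy parameter, by lens, cross-tabulate each eye's baseline grade (as defined in SAP 5.3) against its grade at the lens-off Visit 3/Exit examination. Show the number of eyes that increased by 1 or more grades and by 2 or more grades, and count separately the exposed eyes with no Exit examination. Keep the per-visit tables and the listings. If Sections 6 to 8 already contain this table, a cross-reference from 5.3.2 is enough.

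A version based on each eye's worst grade after exposure should be supplementary only and labelled as such. It pools lens-on and lens-off examinations, and taking the worst of several grades against a single baseline grade overstates worsening through grading variability alone.

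The cost is a few lines of SAP text and one stacked table covering the 11 named parameters, from data already collected. No new examination is needed.

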10.3 Unscheduled Visits

If a subject visit occurs between any regularly scheduled visits, this visit must be documented as an Unscheduled Visit. During all unscheduled visits, the Investigator must conduct the following procedures:

- Collect Adverse Event information
- Record changes in medical condition or concomitant medication
- Collect Device Deficiency information, as applicable
- Assess and record VAs
- Perform biomicroscopy (assessments with or without lenses, as applicable)

The Investigator may perform additional procedures for proper diagnosis and treatment of the subject. The Investigator must document this information in the subject's case history source documents.

If during an Unscheduled Visit the subject is discontinuing the IP or discontinuing from the study, the Investigator must conduct Exit procedures according to Table 3-1, Schedule of Study Procedures and Assessments, as possible.

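### SAP 5.3.2 leaves an exit biomicroscopy done at an unscheduled visit out of the by-lens grade tables, and the visible SAP has no rule for early-exit visits (minor)

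*SAP*

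**What the plan says.** **Analysis rule.** SAP 5.3.2 gives the table rule, "A summary of grade category counts and percentages will be presented for each parameter at each scheduled visit", followed by the listing rule, "Findings collected during unscheduled visits will be presented in a subject listing". The reporting unit is the eye. SAP 2.1 puts every exposed eye in the safety set, classified by the lens worn at the time of assessment. SAP 5.2 describes the aim as a "comprehensive descriptive assessment of safety endpoints listed in Section 5.1", and SAP 5.1 names biomicroscopy there separately from AEs.

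**Visit rules.** Protocol 10.3 states: "If a subject visit occurs between any regularly scheduled visits, this visit must be documented" as an Unscheduled Visit. It continues: "If during an Unscheduled Visit the subject is discontinuing the IP or discontinuing from the study, the Investigator must conduct Exit procedures", following Table 3-1 as far as possible. Protocol Section 10 names a further type: "Unscheduled Visits and Early Termination Visits are allowed, if necessary". Protocol 10.4.3 calls for an Early Exit Visit and refers to Table 3-1. That table has columns only for Visits 1, 2, 3 (Exit) and Unscheduled, and the SAP appendix schedule has the same columns.

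**Protocol analysis text.** Protocol 12.6 says that each parameter is tabulated by grade and sets no limit to scheduled visits. Protocol 12.5 says that all data from evaluable eyes are used.

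**The concern.** Eyes seen off schedule, and eyes whose owner gives up extended wear, are plausibly the eyes with more to see at the slit lamp. Under the SAP rule, an exit examination coded as unscheduled adds nothing to the 1-Week grade table, either as a count or in the denominator. If one lens caused more of the stops, its 1-Week grade distribution would look better than the experience of all eyes exposed to it. The listing keeps the data but gives no frequency by lens.

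Where an early exit is not coded as unscheduled, the visible SAP gives the programmer no rule. The examination could be tabulated with Visit 3, listed, or shown separately, and that choice would be made outside the plan.

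**Working it through.** **1. Where an examination goes under the visible text**

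| Situation | Visit type | SAP 5.3.2 output |
|---|---|---|
| Exit examination between Visits 2 and 3 | Unscheduled (Protocol 10.3) | Listing only |
| Exit at Visit 2 | Scheduled | 1-Day table |
| Lens stopped, subject still attends Visit 3 | Scheduled | 1-Week table |
| Early Termination or Early Exit Visit recorded as such | No column in the schedule | Not stated |

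The gap is definite in the first row, open in the last and absent in the other two.

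**2. Corneal staining.** In Table 3-1 the Visit 2 biomicroscopy carries the mark for an examination with lenses on the eye, which excludes corneal staining. Visit 3 has the marked examination and a further one at Exit. Visit 3 Exit is therefore the only scheduled post-exposure examination that provides for a staining grade. An eye in the first row may have its only post-exposure staining grade in the listing. This is not certain, because Protocol 10.3 allows unscheduled biomicroscopy with or without lenses.

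**3. What the AE tables already catch.** Protocol 11.1 requires reporting of corneal staining at Grade 3 or above, neovascularization at Grade 2 or above, all symptomatic corneal infiltrative events and peripheral non-infectious ulcers. Protocol 11.2 adds untoward changes that the Investigator considers clinically relevant. SAP 5.3.1 presents ocular AEs by eye with relationship to lens. What remains is mainly lower grades and asymptomatic findings not judged clinically relevant.

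**4. The plan's own numbers.** SAP Table 1-1 gives about 22 enrolled and 20 to complete. The gap is 22 − 20 = 2, or 2/22 = 9.1%. No dropout rate is stated, so the 22 cannot be derived independently. Using 20/(1 − d) rounded up, an assumed d of 5% gives 22 and 10% gives 23, both consistent with about 22.

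**5. Illustration.** Assume that 22 subjects are exposed, giving 22 eyes per lens because the design is contralateral, and that every early exit is coded as unscheduled.

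- Two early exits, both with a test-eye finding, and no affected completer: the 1-Week table shows 0/20 = 0%; all exposed eyes give 2/22 = 9.1%.
- Two early exits and one affected completer: the table shows 1/20 = 5.0%; all exposed eyes give 1/22 = 4.5% if neither exit has the finding and 3/22 = 13.6% if both do.
- One early exit with the finding and no affected completer: 0/21 = 0% against 1/22 = 4.5%.

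**The case against.** A reader might infer that the exit examination of every eye that stops early is missing from all grade tables, and that the 1-Week percentages describe completers only. The documents do not support that. Early Termination and Early Exit Visits are unassigned, which is not the same as excluded, and they could be tabulated under the Visit 3 Exit column. An exit at Visit 2 is in the 1-Day table. A subject who stops lens wear but attends Visit 3 is in the 1-Week table.

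A reader might also take 2/22 as the expected size. It is not. The Protocol glossary defines an enrolled subject as anyone who signs consent, and Protocol 10.4.2 counts screen failures among discontinued subjects. The gap between 22 and 20 may therefore include people who never wore a study lens and are outside the safety set.

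It is also fair to say that no data are lost, that a listing of a few subjects can be read line by line, and that the more serious findings reach the AE tables. An any-visit summary whose denominator was every examined eye would bring its own error, since it would count eyes never graded for staining.

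All of this stands, and it reduces the point to a minor one. It does not remove it: the first row of the table above follows from the two stated rules, and a listing gives no grade frequency by lens.

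**Conclusion.** The point holds in a limited form and is minor. An exit biomicroscopy documented as an Unscheduled Visit appears in no by-lens grade table, and the visible SAP does not assign Early Termination or Early Exit Visits to any output. The consequence falls mainly on lower-grade or asymptomatic findings. It is clearest for corneal staining, where the listed grade may be the eye's only one after exposure.

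Few eyes are likely to be affected. The 0/20 against 2/22 contrast needs four assumptions together: both non-completers were exposed, both exited at unscheduled visits, both had a test-eye finding, and no completer had one. It shows what the rule could hide and is not a forecast.

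One limit remains. No text is visible for SAP Sections 6 to 8, and the Manual of Procedures and the Deviations and Evaluability Plan are not available. A visit-assignment rule could be in any of these.

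**What to change.** In SAP 5.3.2, keep the scheduled-visit tables and the listing, and make these additions before unmasking:

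- For each lens and parameter, a summary of the *worst post-exposure grade at any visit*, covering scheduled, unscheduled and early-exit examinations.
- As its denominator, exposed eyes with at least one post-exposure grading of that parameter, so that eyes never graded for corneal staining do not dilute the staining percentage.
- The baseline grade beside it, using the definition in SAP 5.3. Exclusion criterion 4 admits eyes with milder findings, so a post-exposure grade alone does not show change.
- A sentence stating that early-exit examinations are included, with their number.

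Protocol 10.3 already requires biomicroscopy at unscheduled visits, so no new data are needed. The cost is a few lines of SAP text and minor programming. The reported frequencies may be slightly less favourable.
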